COVER PAGE

Official title of the study: Efficacy of Gluma desensitizer in controlling the immediate post treatment sensitivity in etch-and-rinse and self-etch adhesive occlusal composite restorations

NCT04248803

Date of the document: 02-09-2025

Efficacy of Gluma desensitizer in controlling the immediate post treatment sensitivity in etch-and-rinse and self-etch adhesive occlusal composite restorations

NCT04248803

BRIEF SUMMARY

Background

One of the most widely used esthetic restorations in dentistry is composite. Despite the indispensable value that composite brings to a dentist's arsenal, the postoperative sensitivity following composite resin restorations are an undesirable outcome often leading to patient discomfort.

GLUMA desensitizer, a solution containing glutaraldehyde and hydroxyethyl methacrylate (HEMA), is widely used to reduce sensitivity by occluding dentinal tubules and stabilizing collagen fibrils. However, the ideal timing of GLUMA application in different adhesive protocols remains uncertain, raising questions about its effect on postoperative sensitivity, adhesive bond strength, and long-term restoration success.

This clinical trial aims to evaluate the effectiveness of GLUMA in controlling the immediate post treatment sensitivity following occlusal composite restorations. In addition, to compare the difference between the bonding systems (Etch-and-rinse & Self-etch) on reduction of post restoration sensitivity with or without Gluma desensitizer.

Sample Size, Blinding and Randomization

For this clinical trial, a sample size of 504 restorations was calculated to be sufficient for detecting statistical difference using G* power software (α probability error – 0.05 and effect size – 0.2).

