Intervention description for **Arm 4: Self Etch Control group (No desensitizer application)** where no desensitizer was applied after preparing the cavity two coats of Universal adhesive (3M ESPE Single Bond Universal Adhesive, Germany) were applied by scrubbing with a micro brush, for 20 s per coat. When the surface became shiny, it was light-cured for 20s (Woodpecker LED, Guilin, China). After curing the adhesives, placement of Composite (Charisma Smart, Kulzer GmbH, Germany in increments (1–2 mm thick) by layering technique to reduce polymerization shrinkage.

Intervention description for **Arm 5: Self Etch Gluma desensitizer application prior to etching** in this group a small amount of Gluma Desensitizer (Kulzer GmbH, Germany) was applied to the prepared dentin surface for 30-60 seconds, and then gently dried with air until the surface is no longer shiny. Finally, rinse thoroughly with water and suction. Followed by two coats of Universal adhesive (3M ESPE Single Bond Universal Adhesive, Germany) were applied by scrubbing with a micro brush, for 20 s per coat. When the surface became shiny, it was light-cured for 20s (Woodpecker LED, Guilin, China). After curing the adhesives, placement of Composite (Charisma Smart, Kulzer GmbH, Germany in increments (1–2 mm thick) by layering technique to reduce polymerization shrinkage.

Intervention description for **Arm 6: Self Etch Gluma desensitizer application after self-etch adhesive usage** two coats of Universal adhesive (3M ESPE Single Bond Universal Adhesive, Germany) were applied by scrubbing with a micro brush, for 20 s per coat. When the surface became shiny, it was light-cured for 20s (Woodpecker LED, Guilin, China). After curing the adhesives a small amount of Gluma Desensitizer (Kulzer GmbH, Germany) was applied to the prepared dentin surface for 30-60 seconds,

and then gently dried with air until the surface is no longer shiny. Finally, rinse thoroughly with water and suction. Placement of Composite (Charisma Smart, Kulzer GmbH, Germany in increments (1–2 mm thick) by layering technique to reduce polymerization shrinkage.

Outcome measures

The primary outcome of this clinical trial is to evaluate the effectiveness of GLUMA in controlling the immediate post treatment sensitivity following occlusal composite restorations. Hence, all the patients were assessed for post restoration sensitivity after 24 hours, 48 hours and at the end of one week.

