The Kruskal-Wallis test is a non-parametric statistical test used to determine if there's a significant difference between the medians of three or more independent groups. It's an alternative to the one-way ANOVA when the data doesn't meet the assumptions of normality or equal variances.

STATISTICAL ANALYSIS OVERVIEW:

This present study contains six arms whose descriptions have been provided in the brief summary. The statistical analysis was performed using IBM SPSS version 23. The normality was assessed using Shapiro – wilks test and Q -Q plots. Since the groups do not follow the normal distribution Kruskal – Wallis test to test the statistical significance of post operative sensitivity among the groups. Mann – whitney U test was used to assess the post operative sensitivity among the control groups.

GROUPS INVOLVED:

CONTROL GROUPS:

GROUP 1: Total Etch (TE) Control Group

GROUP 2: Self Etch (SE) Control Group

TEST GROUPS:

GROUP 2: TE - GLUMA Application After Acid Etching

GROUP 3: TE - GLUMA Application Prior to Acid Etching

GROUP 5: SE - GLUMA Application Prior to Acid Etching

GROUP 6: SE - GLUMA Application After Acid Etching

NULL HYPOTHESIS:

The null hypothesis states that there is no statistically significant difference in post operative sensitivity on GLUMA application etching before or after total etching or self-etching followed by composite restoration of the carious teeth.

SAMPLE SIZE CALCULATION:

For this clinical trial, a sample size of 504 restorations was calculated to be sufficient for detecting statistical difference using G* power software (α probability error – 0.05 and effect size – 0.2).

TYPE OF ANALYSIS:

The type of trial is a Noninferiority trials. By definition a non – inferiority trial tests whether a new experimental treatment is not unacceptably less efficacious than an active control treatment already in use. With continuous improvements in health technologies, standard care, and clinical outcomes, the incremental benefits of newly developed treatments may be only marginal over existing treatments. (Hahn S. Understanding noninferiority trials. Korean journal of pediatrics. 2012 Nov 23;55(11):403.)

This test is a non - inferiority trial hence the six groups have GLUMA application before etching of a composite restoration which is not unacceptably less efficacious in reducing post operative sensitivity in composite restoration of a carious tooth.

PROCEDURE:

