DESINSENSITIZING AGENT	Pre Op VAS	Post Op VAS (24 hrs)	Post Op VAS (48 hrs)	Post Op VAS (1 week)
	Mean±SD	Mean±SD	Mean±SD	Mean±SD
Total etch control	0.86±1.67	0.37±1.05	0.37±1.05	0.21±0.77
Total etch Gluma prior to etching	1.72±2.15	0.49±1.33	0.40±1.12	0.23±0.81
Total etch Gluma after etching	1.16±2.07	0.28±0.93	0.28±0.93	0.26±0.95
Self etch control	1.88±2.25	0.66±1.32	0.41±1.00	0.12±0.33
Self etch Gluma prior to etching	0.63±1.05	0.20±0.46	0.03±0.16	0.08±0.27
Self etch Gluma after etching	2.11±2.40	0.61±1.31	0.37±0.97	0.21±0.53

- **ESTIMATION PARAMETER:** Mean Difference (Final Values)

ESTIMATED VALUE:

The mean post-operative sensitivity at 1 week was 0.18 units lower in the **Self-etch Gluma prior to etching** group compared to the **Total etch Gluma after etching** group, indicating that the former resulted in reduced sensitivity following restoration.

CONFIDENCE INTERVAL: 95%

NUMBER OF SIDES: 1 – sided

LOWER LIMIT:

Estimation Parameter: Mean Difference (Final Values)

Estimated Value: +0.18

Lower Limit (95% CI, one-sided): +0.003

Parameter Dispersion Type: Standard Deviation

Dispersion Value: 0.1077

The dispersion represents the standard deviation of the difference in mean post-operative sensitivity between the two groups.

Age limits: Patient aged between 15 to 70 years of both the gender were included

Healthy volunteers only/ with disease and why: The reason only healthy individuals are often enrolled because this helps to ensure that any observed effects are specifically related to dentin hypersensitivity and not influenced by other factors, such as an impaired immune response that could be present in individuals with certain systemic conditions.¹²

Investigator's Info:

First name: [name] **Middle name:** Nil **Last name:** [name]

Degree: MDS (Master of Dental Surgery)

[contact]

Email ID: [contact]

College Info: CSI College of Dental Sciences and Research, Madurai (CSICDSR)

(Affiliated under TN [name] University, Chennai, India)

Individual Patient sharing: Individual patient details are often not shared in this research due to concerns about privacy, confidentiality, and potential harm to participants, as well as practical and logistical challenges.¹³

References:

1. Porto I. Postoperative sensitivity on direct resin composite restorations: Clinical practice guidelines. *Indian J. Restor. Dent.* 2012; 1:1–12.

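### The only effect estimate with a confidence limit is at 1 week, one of three primary time points, but the conclusion drawn from it is general and is not supported at 24 hours

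*Combined protocol and SAP*

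**What the plan says.** The Brief Summary gives the aim as "controlling the immediate post treatment sensitivity following occlusal composite restorations". The Outcome measures section of the Detailed Description sets the primary outcome in the same terms and then fixes the times: "all the patients were assessed for post restoration sensitivity after 24 hours, 48 hours and at the end of one week". No section singles out one of the three as the principal time.

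The SAP's Procedure section runs a separate Kruskal-Wallis test at each time and justifies this by calling every time point a distinct endpoint. It reports p = 0.126 at 24 hours, 0.050 at 48 hours and 0.013 at 1 week. The table that follows gives means and SDs for each arm before treatment and at all three post-operative times.

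The Estimated Value entry is the only place with a between-arm difference and a limit. It reads "The mean post-operative sensitivity at 1 week was 0.18 units lower in the" self-etch Gluma prior arm than in the total-etch Gluma after arm, and ends "indicating that the former resulted in reduced sensitivity following restoration". Beneath it stand "Lower Limit (95% CI, one-sided): +0.003" and "Dispersion Value: 0.1077".

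**The concern.** If the three times are distinct endpoints, a limit at one of them says nothing by itself about the other two. The sentence starts from a 1-week figure, but its closing clause speaks of sensitivity after restoration in general. A reader who came for the trial's stated question, immediate sensitivity, will take +0.003 as the answer to it.

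The data for the other two times are in the same table, so the SAP's calculation can be repeated there. If it gave the same reading at each time, the general wording would be harmless. If it did not, the conclusion would claim more than the trial showed.

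**Working it through.** **Inputs.** Means and SDs come from the SAP table of mean scores by arm. The planned 84 per arm comes from the Brief Summary list of arms, and the one-sided 95% level from the Estimated Value entry. Differences are total-etch Gluma after minus self-etch Gluma prior, so a positive value favours the latter.

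**Formulas.** SE = √(SD₁²/n₁ + SD₂²/n₂). Lower limit = difference − 1.645 × SE.

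**The SAP's own figure, 1 week.** Scores are 0.26 ± 0.95 and 0.08 ± 0.27.
- Difference: 0.26 − 0.08 = 0.18.
- SE: √((0.9025 + 0.0729)/84) = 0.1078, against the printed 0.1077.
- Lower limit: 0.18 − 1.645 × 0.1078 = +0.003, as printed.

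So the printed dispersion, which the SAP labels a standard deviation, acts as the standard error of the difference with 84 per arm.

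**24 hours.** Scores are 0.28 ± 0.93 and 0.20 ± 0.46.
- Difference: 0.08.
- SE: √((0.8649 + 0.2116)/84) = 0.1132.
- Lower limit: 0.08 − 0.186 = −0.106 (one-sided p = 0.24).

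**48 hours.** Scores are 0.28 ± 0.93 and 0.03 ± 0.16.
- Difference: 0.25.
- SE: √((0.8649 + 0.0256)/84) = 0.1030.
- Lower limit: 0.25 − 0.169 = +0.081.

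**Before treatment.** Means are 1.16 and 0.63, so the difference is 0.53.

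| Time | Difference | Lower limit, n = 84/84 | Lower limit, n = 86/80 (printed in rank table) |
|---|---|---|---|
| 24 h | +0.08 | −0.106 | −0.105 |
| 48 h | +0.25 | +0.081 | +0.082 |
| 1 week | +0.18 | +0.003 | +0.004 |

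Rounding of the tabulated means and SDs moves the 24-hour limit only between −0.117 and −0.094. The sign of that limit therefore depends neither on rounding nor on which of the two sample sizes is used.

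**The case against.** Much can be said for the SAP here. One week is itself one of the primary time points, so the estimate does not use a foreign endpoint, and the documents do not rank 24 hours above the others. The sentence opens by naming 1 week. The 24-hour and 48-hour results are not hidden: means, SDs and a test are given at each time, and the 24-hour test is labelled not significant. All of this stands. It narrows the gap to a missing difference and limit at two times and an over-general closing clause. It does not make that clause true at 24 hours.

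A reader might infer four stronger things that the documents do not support.

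- *That the most favourable time was picked.* The 48-hour estimate is larger and its limit further from zero, so the printed figure is not the best available.
- *That 24 hours contradicts the claim.* The difference has the same sign as at the other times. A lower limit below zero is inconclusive, not contrary.
- *That the arm did worse at 24 hours on ranks.* Its mean rank is higher (125.30 against 117.62), but these are joint ranks over six arms from a non-significant test, not a comparison of the pair.
- *That the 1-week result is overturned.* The mean ranks average 126.5, which fits 252 ranked records rather than 504. With 43 and 40 per arm the limits would be −0.182, +0.013 and −0.068. That discrepancy in N is a separate matter and is not settled by the documents, so nothing here rests on it.

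It is also fair to object that adding rows does not repair the contrast. It compares two Gluma arms, so at no time does it answer whether Gluma works against no desensitizer. The pair also differed before treatment, and the limits use normal theory on data that the Procedure section calls non-normal. This stands too. It is a reason to show the extra rows with those caveats, and not to read the 48-hour row as a demonstrated effect.

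**Conclusion.** The conclusion is wrong as written. The primary outcome covers three times, a difference with a limit is given at one, and the closing clause generalises from it. By the SAP's own method the contrast is +0.08 (limit −0.106) at 24 hours, +0.25 (+0.081) at 48 hours and +0.18 (+0.003) at 1 week. A general statement of reduced sensitivity is therefore not supported at 24 hours, although the direction is the same at all three times.

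The pre-operative difference of 0.53 has the same direction and is larger than any post-operative difference. Even where a limit lies above zero, the words "indicating that the former resulted in reduced sensitivity following restoration" attribute to treatment a gap that was present beforehand. The Procedure section's remark that this arm scored lowest throughout includes the pre-operative mean.

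The figures assume the tabulated means and SDs, 84 per arm (86 and 80 change nothing of substance) and the SAP's normal-theory one-sided limit. They are not adjusted for baseline or for three time points.

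**What to change.** In the Estimated Value entry:

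1. Report the mean difference and its one-sided limit for this contrast at 24 hours, 48 hours and 1 week.
2. Show the pre-operative difference (0.53) beside them.
3. State that the limits are adjusted neither for multiple time points nor for baseline, and that they use normal theory on data the Procedure section describes as non-normal.
4. Replace the closing clause with a statement for each time point, saying that the 24-hour difference is inconclusive and making no claim of effect from the unadjusted limits.
5. Do not present the 1-week limit as the result for immediate sensitivity as a whole.

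The cost is small: two more post-operative rows and one pre-operative difference, all from means and SDs already tabulated, and one rewritten clause. The downside is a less sweeping conclusion. The change is not simply a less favourable one, since the 48-hour row is stronger than the printed one.

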All statistical analyses were performed using non-parametric tests due to the non-normal distribution of the data, as confirmed by both the **Kolmogorov–Smirnov** and **Shapiro–Wilk** tests

($p < 0.001$). Descriptive statistics including mean and standard deviation (Mean \pm SD) were calculated for each of the six desensitizer groups at different time points: Pre-operative, 24 hours, 48 hours, and 1 week post-operative sensitivity, measured using the Visual Analog Scale (VAS).

For intergroup comparisons across all six desensitizer protocols, the **Kruskal–Wallis test** was used independently for each time point. This non-parametric method was selected to assess statistically significant differences in median VAS ranks among the groups, given the violation of normality assumptions. A separate p -value was generated for each time point:

- Pre-operative VAS: $p = 0.003$ (significant)
- 24-hour VAS: $p = 0.126$ (not significant)
- 48-hour VAS: $p = 0.050$ (borderline)
- 1-week VAS: $p = 0.013$ (significant)

Pairwise comparisons between the **Total-etch control** and **Self-etch control** groups were performed using the **Mann–Whitney U test**. This analysis revealed a statistically significant difference in pre-operative VAS scores ($p = 0.012$), while post-operative scores showed no significant differences at 24 hours ($p = 0.337$).

Mean pain scores (VAS) were also summarized for each group at all four-time intervals. The **self-etch Gluma prior to etching group consistently showed the lowest VAS scores** at all time points, suggesting reduced post-operative sensitivity in this group.

Given the minimal differences in outcome scores among the other groups, and the slightly better performance of the self-etch GLUMA prior to etching group, the data suggest that **most treatment protocols were non-inferior** to the best-performing group. Therefore, the trial was interpreted as

a **non-inferiority study**, evaluating whether the other etching and desensitizing protocols were not clinically worse than the most effective group.

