A significance level of $p < 0.05$ was considered statistically significant throughout the analysis. In the present study, the Kruskal-Wallis test was used to compare six desensitizer groups at different time intervals (Pre-operative, 24 hours, 48 hours, and 1 week post-operatively) based on Visual Analog Scale (VAS) scores. Since each time point represents a distinct clinical endpoint, a separate Kruskal-Wallis test was conducted for each, yielding **individual p-values** corresponding to each time point. As the Kruskal-Wallis test does not permit aggregation of multiple outcomes into a single p-value, **a common p-value is not statistically appropriate**.

Ranks

	Desensitizer Group	N	Mean Rank	P Value ^a
Pre Op VAS	Total etch control	86	105.48	0.003
	Total etch Gluma prior to etching	94	141.70	
	Total etch Gluma after etching	86	116.12	
	Self etch control	82	142.30	
	Self etch Gluma prior to etching	80	106.20	
	Self etch Gluma after etching	76	147.55	
	Total	504		
Post Op sensitivity 24hr VAS	Total etch control	86	125.47	0.126
	Total etch Gluma prior to etching	94	122.94	
	Total etch Gluma after etching	86	117.62	
	Self etch control	82	136.49	

	Self etch Gluma prior to etching	80	125.30	
	Self etch Gluma after etching	76	132.62	
	Total	504		
Post Op sensitivity 48hr VAS	Total etch control	86	131.74	0.050
	Total etch Gluma prior to etching	94	127.98	
	Total etch Gluma after etching	86	123.48	
	Self etch control		132.76	
	Self etch Gluma prior to etching	80	114.36	
	Self etch Gluma after etching	76	128.18	
	Total	504		
Post Op sensitivity 1 week VAS	Total etch control	86	124.24	0.013
	Total etch Gluma prior to etching	94	130.96	
	Total etch Gluma after etching	86	124.38	
	Self etch control	82	129.76	
	Self etch Gluma prior to etching	80	115.00	
	Self etch Gluma after etching	76	134.53	
	Total	504		

p < 0.05 denotes statistically significant difference. All the values exhibit non – statistically significant difference. Statistical test applied *

Kruskal – Wallis test

Ranks

	Desensitizer Group	N	Mean Rank	*P Value
Pre Op VAS	Total etch control	86	36.83	0.012
	Self etch control	82	48.45	

	Total	168		
Post Op sensitivity 24hr VAS	Total etch control	86	40.67	0.337
	Self etch control	82	44.41	
	Total	168		

p< 0.05 denotes statistically significant difference. All the values exhibit non – statistically significant difference except the pre operative pain scores. Statistical test applied * Mann Whitney U test

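### The only numerical effect estimate is a normal-theory mean difference on mostly zero scores, although the SAP declares non-parametric analysis, and the mean and rank tables disagree on the arm it favours

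*Combined protocol and SAP*

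**What the plan says.** - **Procedure:** "All statistical analyses were performed using non-parametric tests due to the non-normal distribution of the data". The same section also summarises each arm by mean and SD.
- **Statistical Analysis Overview and Procedure:** Kruskal-Wallis compares the six arms at each time. Mann-Whitney compares only the total-etch and self-etch controls.
- **Definition:** Kruskal-Wallis is described as looking for a "significant difference between the medians of three or more independent groups".
- **Significance level:** p below 0.05 "was considered statistically significant throughout the analysis".
- **Effect estimate, after the mean±SD table:** "Estimated Value: +0.18", "NUMBER OF SIDES: 1 – sided", "Lower Limit (95% CI, one-sided): +0.003", "Dispersion Value: 0.1077". The contrast is self-etch Gluma-prior against total-etch Gluma-after at 1 week, and the text reads it as "indicating that the former resulted in reduced sensitivity following restoration".
- **Outcome measures:** VAS above 3 is the cut for patients who count towards the 1-week results. No table reports that count.

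**The concern.** The SAP sets normal-theory methods aside and then draws its one quantified conclusion from a normal-theory limit. The SDs are more than three times the means (0.26±0.95 and 0.08±0.27), so the comparison rests on a handful of non-zero scores and the limit clears zero by 0.003. A reader would take the 0.18 as supported by the declared rank analysis, but no rank result for this pair is given. If the tables behind the estimate also describe different data for the favoured arm, the claim has no settled basis.

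**Working it through.** **1. Reproduce the printed figures.** Inputs are the 1-week mean±SD and the planned 84 per arm.
- Difference: 0.26 - 0.08 = 0.18.
- SE: sqrt(0.95²/84 + 0.27²/84) = 0.1078 (printed as 0.1077). The printed dispersion is therefore the standard error of the difference.
- One-sided limit: 0.18 - 1.645 × 0.1078 = 0.003.

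This is a large-sample z-limit on means. The two-sided 95% interval from the same SE is 0.18 ± 1.96 × 0.1078, or -0.03 to 0.39 (p = 0.095).

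**2. Number of records behind the ranks.** Ranks of N records must sum to N(N+1)/2.
- Labelled N (86, 94, 86, 82, 80, 76) times the 1-week mean ranks: 63,756. For 504 records, 504 × 505/2 = 127,260 is needed.
- Half the labelled N (43, 47, 43, 41, 40, 38): 31,878 = 252 × 253/2.

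The ranks therefore come from 252 records, with 43 and 40 in the two arms of interest. At those sizes SE = sqrt(0.95²/43 + 0.27²/40) = 0.151, and the one-sided limit is 0.18 - 1.645 × 0.151 = -0.07.

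**3. Rank test on scores that match the mean table.** Assume whole numbers from 0 to 10. The protocol describes a 1-10 scale, but means below 1 require zeros. P-values are two-sided and tie-corrected.
- Self-etch Gluma-prior, n = 40: three 1s is the only fit (3/40 = 0.075; SD 0.27).
- Total-etch Gluma-after, n = 43: the total is 11 and the sum of squares is 41. Only {4,4,3} and {6,1,1,1,1,1} fit, with zeros otherwise.

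| Records | Total-etch Gluma-after | Self-etch Gluma-prior | Mann-Whitney |
|---|---|---|---|
| 43/40 | {4,4,3} | three 1s | U = 3×40 + 0.5×40×37 = 860 = 43×40/2; p = 1.00 |
| 43/40 | {6,1,1,1,1,1} | three 1s | U = 40 + 5×(37+1.5) + 0.5×37×37 = 917; p = 0.34 |
| 86/80 | 21 sets, 6 to 13 non-zero scores | six 1s | p from 0.11 to 1.00 |

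**4. What the rank table implies.** Self-etch Gluma-prior has a 1-week mean rank of 115.00 = (229 + 1)/2, the shared rank of 229 tied zeros. Non-zero counts of 3, 6, 3, 5, 0 and 6 (in table order) leave 252 - 23 = 229 zeros and reproduce all six printed mean ranks to two decimals. In that version:
- the favoured arm has no non-zero score, against three 1s in the mean table;
- this pair gives U = 3×40 + 0.5×40×40 = 920 against 860 expected, p = 0.09;
- p falls to 0.016 only if every record is counted twice;
- the six-arm Kruskal-Wallis p is 0.207 on 252 records, and 0.013 as printed only with every record doubled.

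With 43/40 records, no combination of whole-number scores that matches the mean table in all six arms reproduces the printed ranks.

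**5. Ordering of arms.** Six arms give 15 pairs at each of three post-operative times, 45 in all. The mean and rank tables order 10 oppositely: three at 24 h, two at 48 h and five at 1 week. Total-etch Gluma-prior against its own control is among them twice:
- 24 h: higher by mean (0.49 v 0.37), lower by mean rank (122.94 v 125.47);
- 48 h: higher by mean (0.40 v 0.37), lower by mean rank (127.98 v 131.74).

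**The case against.** **The mean difference is a legitimate summary.** The SAP declares non-parametric tests, and it also plans means and SDs. A mean difference keeps intensity, which a count of any sensitivity discards. With {4,4,3}, the protocol's cut of VAS above 3 would give 2/43 against 0/40. This stands, and it is a reason to keep the 0.18 as description. It does not support an inference from a z-limit on so few non-zero scores.

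**The printed ranks point the same way as the 0.18.** At 1 week the mean ranks are 124.38 and 115.00, which favours self-etch Gluma-prior. This also stands, but the rank-table version gives p = 0.09 on the records that the ranks describe.

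**Opposite orderings need not be errors.** Means and ranks can differ honestly on skewed scores. The ten pairs show that the choice of scale matters here. The conflict over the favoured arm is a different matter, because one set of 40 scores cannot be both three 1s and all zeros.

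**A stronger reading is not supported.** A reader might infer that the SAP's own rank test shows exactly no difference, with three sensitive patients in each arm. The SAP reports no rank test of this pair and no such counts. The value p = 1.00 needs the undeclared 43/40 records and a choice of {4,4,3} over the other fit. The printed mean rank of 124.38 would favour {4,4,3}, but the same rank table contradicts three non-zero scores in the comparator arm. Nor is 0.18 the only claim of benefit: the Procedure section makes a qualitative one for the same arm. It is the only numerical one.

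**Conclusion.** The point holds as an inconsistency of method together with two tables that cannot both be right. The 0.18 with limit +0.003 is a z-limit on means, reported under a plan that declares rank methods, with no rank test of the pair. No whole-number data set that matches the mean table reaches p < 0.05 by Mann-Whitney: p is 1.00 or 0.34 at 43/40 records and 0.11 to 1.00 at 86/80. The rank-table version reaches it only by counting each record twice (p = 0.016, against 0.09 undoubled). The limit itself turns negative (-0.07) at 43/40.

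Reading the 0.18 as reduced sensitivity is therefore unsupported. The documents do not show that the two arms are equal. The z-limit and the rank-sum check use printed figures only. The Mann-Whitney results also assume whole-number scores with zero allowed, and which of them applies depends on the true number of records, which only source data can settle.

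**What to change.** 1. Withdraw the reading of the 0.18 as reduced sensitivity, and keep the mean difference as description only.
2. Reconcile the mean±SD and rank tables with source data, starting with self-etch Gluma-prior at 1 week, and state the true number of records.
3. For each arm and time, report the number and percentage with any sensitivity and with VAS above 3.
4. Give contrasts on a scale that matches the test: probability of superiority beside Mann-Whitney, or a risk difference with Newcombe limits for the counts.
5. As a minor wording change, describe Kruskal-Wallis as a test of equal distributions.

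The cost is one re-run on existing data and a less favourable headline. A risk difference gives up some information on intensity, which the VAS above 3 count and the descriptive mean partly restore.

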Post –operative sensitivity after 24 and 48 hours were assessed with VAS score (1- 10) through telephonic call by a resident student who are unaware of the treatment allocation group. The Visual Analogue Scale (VAS) is a common and effective tool for assessing pain and other subjective symptoms, including postoperative sensitivity. In this study a 1-10 scale were used and the patient is asked to choose a number ranging from 1 to 10 based on their sensitivity, with 1 being the least sensitivity and 10 being the most. The advantages of VAS scale is its simplicity, ease of use and applicability.

Post-operative sensitivity after one week all the patients were recalled and clinically assessed by Schiff cold air sensitivity scale by an Experienced Post Graduate Supervisor (EPGS) who is unaware of the allocated treatment groups and those patients with post-operative sensitivity of VAS > 3 were considered for the results (Berkowitz G *et al* 2013)¹¹. A statistician also looked at the treatment results without knowing anything about them.

Schiff cold air sensitivity scale is used to check for post-operative sensitivity which measures a patient's response to a cold air stimulus, helping to gauge the level of sensitivity in a tooth. The procedure involves directing a stream of air at the tooth and observing the patient's reaction, with scores ranging from no response to severe pain (intensity) requiring immediate discontinuation of the stimulus.

The secondary outcome was to assess whether patient had post-operative sensitivity due to any trigger stimulus. This was assessed at the end of 24 hours, 48 hours and one week post-operatively. At 24 hours and 48 hours through telephonic call a resident student who is unaware of the treatment allocation group questioned the patients those who had post-operative sensitivity whether the sensitivity is due to any stimuli (upon mastication/ intake of hot or cold) or spontaneous.

At the end of one week the patients were recalled checked for post-operative sensitivity using both Schiff Air Scale and those patients with post-operative sensitivity of VAS > 3 were questioned whether sensitivity is due to any stimuli¹¹ (upon mastication/ intake of hot or cold) or spontaneous.

STATISTICAL ANALYSIS PLAN

DEFINITION:

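### The only confidence limit in the SAP, a one-sided lower limit, does not support the conclusion that most protocols were non-inferior to self-etch Gluma prior to etching

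*Combined protocol and SAP*

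**What the plan says.** The SAP's Type of Analysis section states "The type of trial is a Noninferiority trials" and gives a general definition. It then describes Gluma applied before etching as the treatment that is not unacceptably less efficacious. The Procedure section sets a different comparison: whether the other protocols are clinically no worse than the best-performing group, self-etch Gluma prior to etching. It concludes that "most treatment protocols were non-inferior" to that group. No non-inferiority margin appears anywhere in the document.

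The estimation block after the table of means and SDs reports one contrast:
- The text begins "The mean post-operative sensitivity at 1 week was 0.18 units lower in the" self-etch Gluma prior arm, compared with total-etch Gluma after etching.
- The entries are "Estimated Value: +0.18", "CONFIDENCE INTERVAL: 95"%, "NUMBER OF SIDES: 1 – sided" and "Lower Limit (95% CI, one-sided): +0.003".
- The dispersion is 0.1077, described as the standard deviation of the difference in means, so it is a standard error.

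The Outcome measures section gives the direction of the scale: "with 1 being the least sensitivity and 10 being the most". Higher is worse.

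**The concern.** To claim that an arm is not unacceptably worse than a reference, one must limit how much worse it could be. With higher scores worse and the difference taken as arm minus reference, that is the upper confidence limit, judged against a margin. The SAP reports the lower limit, which says how small the disadvantage could be and leaves its largest plausible size open.

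The reported limit therefore does not answer the question posed in the Procedure section, although it is the only interval given in a SAP that declares a non-inferiority trial. The conclusion covers most of five arms, yet four of them have no interval at all. A reader could take the trial to have ruled out a meaningful disadvantage for several protocols when the document shows no such result.

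**Working it through.** **Inputs.** The 1-week means and SDs come from the SAP table: total-etch Gluma after 0.26 (SD 0.95) and self-etch Gluma prior 0.08 (SD 0.27). The standard error is the stated 0.1077. Planned n is 84 per arm; the 1-week Kruskal-Wallis table gives 86 and 80 for these two arms.

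**Subtraction order.** 0.26 − 0.08 = +0.18, so the entry is total-etch Gluma after minus self-etch Gluma prior, and positive means the comparator is worse.

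**Standard error.** √(0.95²/84 + 0.27²/84) = 0.1078, matching the stated 0.1077 up to rounding. With 86 and 80 it is 0.1068.

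**Reported limit.** 0.18 − 1.645 × 0.1077 = +0.0028, which rounds to the stated +0.003. The figure reproduces.

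**Missing limit.** 0.18 + 1.645 × 0.1077 = +0.357. Pooled or unpooled SE, z or t quantiles, and planned or tabulated n all give +0.36 to two decimals.

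**Two-sided 95% interval.** 0.18 ± 1.96 × 0.1077 = −0.031 to +0.391.

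**All five arms against self-etch Gluma prior.** d = arm mean − 0.08; SE = √(SD²/n + 0.27²/80), with tabulated n; one-sided upper limit = d + 1.645 × SE; two-sided interval = d ± 1.96 × SE.

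| Arm | n | Mean (SD) | d | SE | One-sided 95% upper | Two-sided 95% |
|---|---|---|---|---|---|---|
| Total-etch control | 86 | 0.21 (0.77) | 0.13 | 0.0883 | 0.275 | −0.043 to 0.303 |
| Total-etch Gluma prior | 94 | 0.23 (0.81) | 0.15 | 0.0888 | 0.296 | −0.024 to 0.324 |
| Total-etch Gluma after | 86 | 0.26 (0.95) | 0.18 | 0.1068 | 0.356 | −0.029 to 0.389 |
| Self-etch control | 82 | 0.12 (0.33) | 0.04 | 0.0473 | 0.118 | −0.053 to 0.133 |
| Self-etch Gluma after | 76 | 0.21 (0.53) | 0.13 | 0.0679 | 0.242 | −0.003 to 0.263 |

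Taking most to mean at least three of five, the third-smallest upper limit is 0.275. A margin of about 0.28 or more would be needed, which exceeds the 1-week mean of either no-Gluma control arm (0.21 and 0.12).

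**Which N applies.** The 1-week mean ranks, weighted by tabulated n, average 126.5. Ranks of N observations average (N + 1)/2, so N = 2 × 126.5 − 1 = 252; 504 observations would average 252.5. If the real numbers are about half those tabulated (43 and 40), the SE is √(0.95²/43 + 0.27²/40) = 0.151. The one-sided limits become 0.18 ± 1.645 × 0.151 = −0.07 and +0.43.

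**The case against.** Which side is relevant depends on which section governs. The Type of Analysis wording can be read with Gluma before etching as the tested treatment. Then total-etch Gluma after minus self-etch Gluma prior, with a lower limit, is the right side, and +0.003 would meet any positive margin for that pair. A reader might infer that the limit is useless for non-inferiority on every reading; the documents do not support that. What remains is that the two sections disagree on the tested arm. The Procedure section is the only place with an explicit reference group and a conclusion, and that conclusion concerns the other arms.

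The Procedure section also does not cite this limit. It argues from small differences in scores and speaks only of most protocols, and the contrast reported uses the arm with the highest 1-week mean, which could fall outside that majority. A lower limit above zero can also coexist with non-inferiority inside a margin. So the limit does not refute the conclusion. It leaves it unsupported, because small observed differences without an upper limit and a margin do not establish non-inferiority.

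A reader might also see a conflict between a score described as 0.18 lower and an entry of +0.18. There is none once the subtraction order is recovered; the order is merely unstated.

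**Conclusion.** The point holds as a mismatch between the reported limit and the Procedure section's conclusion. On that section's question the relevant limit is about +0.36, it is not reported, and the other four arms have no interval.

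A reader might go further and infer that +0.003 shows total-etch Gluma after to be worse. The documents do not firmly support that. The limit clears zero by 0.003; a pooled SE at 86 and 80 (0.110) gives −0.001; the two-sided interval includes zero; and at half the tabulated n the lower limit is −0.07. The contrast also sets the highest of six means against the lowest with no stated multiplicity control, and pre-operative VAS differed between arms (p = 0.003).

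Nor does +0.36 show inferiority: with no margin it cannot be judged.

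These figures rest on the tabulated means and SDs, the normal approximation that reproduces the SAP's own limit, and the tabulated or planned n. The relevance of the upper side does not depend on which n is right; the width does.

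**What to change.** - Reconcile the Type of Analysis and Procedure sections on which arm is tested and which is the reference.
- State the subtraction order once: arm minus self-etch Gluma prior, positive meaning worse.
- Verify the number analysed in each arm. Then report the difference and two-sided 95% interval for all five arms against self-etch Gluma prior, in place of the single one-sided limit.
- Present these as difference estimates and do not cite them for non-inferiority.
- Withdraw the statement that most protocols were non-inferior. No margin is stated, and the Procedure section derives the label from the observed scores. Adding the upper limit alone would not rescue the claim, and a margin chosen now would be chosen with the results known.

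The cost is a check of the per-arm numbers and re-reporting from data already held; no new data are needed. The downside is a less favourable conclusion: small estimated differences, with intervals that at the tabulated n all include zero, and no non-inferiority finding.
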